Review of glucose diary and			Χ	X	Х	Х	Х	X	Х	Х		
hypoglycemic protocol and												
reporting form												
Assessment of response ^h					Χ				Х			
PROMIS questionnaires, SF36,	Х			Х	Х	Х		Х	Х	Х		
PROBE												
Study drug dispensation		Χ			X ⁱ	Χ						
Study drug collection										X^{j}		

^a Clinical PDAI excluding pouchoscopy

^bCBC, AST, ALT, AP, Bilirubin, Creatinine, CRP. Serum samples for GLP-1 baseline fasting if possible (Screening or week 0).

^c Subject diary will be maintained electronically and completed daily reporting stool frequency, rectal bleeding, fecal urgency or abdominal cramps, and/or fever. The patient will complete this diary each day, beginning with the screening visit and ending at the visit. The average 7-day bowel frequency will be calculated for each 7-day period. For the clinical PDAI scores the last three days of diary entries before each visit will be used to calculate stool frequency and fecal urgency/abdominal pain scores.

^d Phone visit only with review of diaries and dose increase of study drug if tolerated. Patient will mail stool sample calprotectin or bring in person.

^f Crossover occurs after at least 5 days of washout after the last study dose

^g Pregnancy test at week 4 in case of early crossover

h Assessment of response: If average weekly bowel frequency of patient did not decrease by at least 15% compared to baseline the patient can proceed to early crossover (Period 1 week 4) or early termination (Period 2 week 10).

Non-responder at Period 1 week 4 receive study drug for period 2 to start 5 days after the last study dose of period 1

^jCollection of study drug from non-responders in Period 2 week4 and all patients who were responding at Period 2 week 10 and completed study at Period 2 week 12.

^k For non-responders at Period 2 week 10 the safety outcomes below will be assessed at Period 2 week 12. For this patient group at Period 2 week 12 only adverse events (review adverse events diary) and concomitant medication will be assessed at Period 2 week 12. An alternative approach is a phone visit at Period 2 week 12 (similar to the final visit at Period 2 week 14) and patient returns all study medication from period 1 and 2 before Period 2 week 12.

REFERENCES

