- 2. To study safety, tolerability and quality of life in the trial period of liraglutide vs placebo application
- 3. To collect first data about the efficacy of a liraglutide therapy in patients with an ileo-anal pouch anastomosis (IPAA) and abnormal high bowel frequency in the absence of inflammation for planning a larger phase 3 study in this orphan status patient population

STUDY DESIGN

Randomized, double-blind, 2-period, placebo- controlled, crossover proof of concept study. Ten patients with increased bowel frequency is defined as > 8 bowel daily/week without significant pouchitis* will be randomized to either liraglutide or placebo treatment for 6 weeks (Period 1). Subjects will be randomized 1:1 to 1 of 2 treatment sequences, liraglutide-placebo or placebo-liraglutide, and receive either liraglutide or volume-matched placebo. After a washout period of at least 5 days (the half-life of liraglutide is 11-12 hours, thus the minimal washout period of 5 days is equal to 10 half-life's) patients will be crossed over to the other treatment arm (Period 2). Since high bowel frequency can result in significant malaise and dehydration, patients not responding to the respective therapies in period 1 may be crossed over after 4 weeks of therapy or in period 2 can be terminated early at week 4. The rationale behind the early termination is based on 2 open label cohorts reporting the efficacy of liraglutide or exenatide in patients with high output ileostomies (the patient group the most comparable to the pouch patient population). GLP-1 receptor agonist therapy even at the lowest dose showed an almost immediate effect reducing the ostomy output after 1-3 days in most patients.^{26, 27} Thus, patients not responding to a 4-week therapy with a GLP-1receptor agonist are highly unlikely to respond if the therapy would be continued.

[figure not shown]

Figure 3: Study design

Randomization: Subjects will be randomized 1:1 to 1 of 2 treatment sequences, liraglutide—placebo or placebo—liraglutide, and receive either liraglutide or volume-matched placebo.

STUDY DRUG, SUPPLY OF STUDY DRUG AND RECRUITMENT PLAN

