The Pouchitis Disease Activity Index (PDAI) was developed by Sandborn et al for diagnosing active pouchitis and quantifying the severity of pouchitis ³⁶. Shen et al. later on modified the index (mPDAI) and showed that similar outcomes can be measured after omitting the evaluation of histology, thus omitting the biopsy and histology costs. ³⁵ The PDAI or the modified PDAI has been used in a number of clinical studies where it appears quite useful in discriminating between subjects with and without pouchitis and in quantifying the severity of pouchitis ³⁷⁻⁴⁵ The mPDAI will be evaluated based at screening, week0,2,4,6,7,8,10,12.

- Stool calprotectin (assessment of pouch inflammation over time)
 Calprotectin, a member of the S100 family of calcium-binding proteins is abundant in the stool and its level correlates with the endoscopic degree of intestinal inflammation in patients with ulcerative colitis and pouchitis. 46,47 Calprotectin can be quantified in feces using enzyme-linked immunosorbent assay (ELISA) or an immunoassay. We will collect stool samples for the measurement of calprotectin at the screening visit and on weeks 2,4,6,8,10,12.
- 36-Item Short Form Health Survey (SF-36)
 The SF-36 will be evaluated at screening, week 2,4,6,8,10 and 12.
- PROMIS measures for incontinence⁴⁸

The GI-PROMIS scales belong to the PROMIS system, which was created by the National Institutes of Health (NIH) to allow efficient, online measurements of patient reported outcomes and correlate with other established quality of life measures.^{48, 49} The PROMIS scale for incontinence will be evaluated at screening, week 2,4,6,8,10 and 12.

- PROBE score⁵⁰
 - PROBE assesses the psychosocial burden of IBD and has been recently validated.⁵⁰ PROBE will be evaluated at screening, week 2,4,6,8,10 and 12.
- Body weight and visual analogue scales for nausea, appetite, abdominal pain and well being²⁵ Body weight will be evaluated at screening and on weeks 4,6,10,12.

OVERVIEW OF TRIAL SEQUENCE

Screening visit (site visit): The trial will begin with the screening visit (days -14 to -10). The investigator will ask patients who are interested in participating in the study after a careful explanation, to sign an informed consent form prior to study specific examinations. The study patient will receive a copy of the consent form, which outlines the sequence of events in brief and summarizes the advantages and disadvantages of participation in the study.

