If at visit week 4 the bowel frequency of the patient did not respond to treatment (at least a 15% decrease compared to baseline the patient can proceed to early crossover. The patient will be given study drug (either the placebo or the liraglutide group) in medication packs with his unique study ID medication packs, which will be containing treatment until week 12 and be instructed to bring back the study medication from study period 1 at the final visit of period 2 (week 12). He will be instructed to start injections on day 6 after 5 days of washout. The day he starts will be defined as week 6 period 2.

Visit week 6 period 1 (site visit): If the patient did not qualify for early crossover, he will come to visit week 6 period 1 the coordinator will review the adverse events, which occurred since the previous visit. A physical exam and blood tests will be performed and the mPDAI will be calculated. The concomitant medications will be assessed. If subject is a woman of child-bearing potential, a reliably and highly effective contraceptive method will be confirmed. A stool sample will be collected from the patient either at visit or days -2 - +2 around the study visit as mail in. Female patients will provide urine samples for pregnancy test at week 6 period 1. The patient will be given either the placebo or the liraglutide group with his unique study ID for period 2 and will be instructed to start injections on day 6 after 5 days of washout. The day he starts will be defined as week 6 period 2. The patients will be also be instructed to bring back the study medication from study period 1 at the final visit of period 2 (week 12). There will also be a review of glucose diary and hypoglycemic protocol and reporting form.

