We will perform exploratory analyses using descriptive statistics (mean, median, standard deviation, minimum, and maximum) and bivariate analyses of the values at each assessment and the change from baseline to each assessment. In the evaluation of the PROMIS measure for incontinence, PROMIS measures utilize a T-score metric where a score of 50 is the mean of a relevant reference population and 10 is the standard deviation. Additionally, a clinically minimally important difference is reflected by a change of 2.

Missing data

Due to short and intensive period of follow-up for the primary outcome, we do not anticipate significant missing data.

SAMPLE SIZE CALCULATION

The analysis will be based on the within-subject difference between two one-week averages of the number of bowel movements per day (BMPD). A one-sample t-test will be used to test the

null hypothesis that the mean difference is zero. With a sample size of 10 subjects and Type-I 0.05 (2-sided), the power is 0.80 against a difference of 1 standard deviation (SD) of the difference (not SD of the individual outcomes). The first average within each patient, by design, will be greater than 8 BMPD, and the range is most likely to be 8-11. The standard deviation (SD) of such an outcome can't (mathematically) exceed 1.5, and this will be used in the sample size calculations as the SD of each weekly average (control and treatment). Additionally, the SD of the difference depends on the correlation between the two weekly averages. Taking that into account, the power is 0.80 against a difference of 2.1 BMPD if the correlation is 0, 1.8 BMPD if the correlation is 0.25, 1.5 BMPD if the correlation is 0.50, 1.1 BMPD if the correlation is 0.75. Assuming a baseline average of 10 BMPD, the design has good power against relative changes of 21% or higher if the within-subject correlation is zero. The power increases with increasing positive correlation and, naturally, is higher against larger effects. If patients drop out during the study the power will decrease, however patents will be carefully selected and thus dropouts are unlikely to occur.

FUTURE PERSPECTIVE

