APPENDIX B: SF-36

36-Item Short Form Survey Instrument (SF-36)

RAND 36-Item Health Survey 1.0 Questionnaire Items

Choose one option for each questionnaire item.

1. In general, would you say your health is:
1-Excellent
2-Very good
○ 3 - Good
○ 5 - Poor
2. Compared to one year ago, how would you rate your health in general now?
2. Compared to one year ago, how would you rate your health in general now? 1- Much better now than one year ago
1- Much better now than one year ago
1- Much better now than one year ago 2- Somewhat better now than one year ago

The following items are about activities you might do during a typical day. Does **your health now limit you** in these activities? If so, how much?

	Yes, limited a lot	Yes, limited a little	No, not limited at all
3. Vigorous activities , such as running, lifting heavy objects, participating in strenuous sports	O 1	O 2	3
4. Moderate activities , such as moving a table, pushing a vacuum cleaner, bowling, or playing golf	O 1	O 2	3
5. Lifting or carrying groceries	 	O 2	3
6. Climbing several flights of stairs	 	O 2	3
7. Climbing one flight of stairs	 	O 2	3
8. Bending, kneeling, or stooping	 	O 2	3
9. Walking more than a mile	 	O 2	3
10. Walking several blocks	 	O 2	3
11. Walking one block	 	O 2	3
12. Bathing or dressing yourself	 	O 2	3

During the **past 4 weeks**, have you had any of the following problems with your work or other regular daily activities as a result of your physical health?

 13. Cut down the amount of time you spent on work or other activities 14. Accomplished less than you would like 15. Were limited in the kind of work or other activities 16. Had difficulty performing the work or other activities (for example, it effort) 	t took e	xtra	Yes 1 1 1 1 1 1 1 1 1	2 2 2 2 2 2
During the past 4 weeks , have you had any of the following proof other regular daily activities as a result of any emotional prob ed depressed or anxious)?		-		or
	Yes	No		
17. Cut down the amount of time you spent on work or other activities	 	O 2		
18. Accomplished less than you would like	 	O 2		
19. Didn't do work or other activities as carefully as usual	 	O 2		
20. During the past 4 weeks, to what extent has your physical has problems interfered with your normal social activities with fan groups? 1- Not at all 2- Slightly 3- Moderately 4- Quite a bit 5- Extremely				, or

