Liraglutide therapy in patients with IPAA and chronic high bowel frequency

21. How much bodily pain have you had during the past 4 weeks ?
1-None
2-Very mild
○ 3-Mild
○ 4 - Moderate
○ 5 - Severe
○ 6 - Very severe
22. During the past 4 weeks , how much did pain interfere with your normal work (including both work outside the home and housework)?
(including both work outside the home and housework)?
(including both work outside the home and housework)? 1-Not at all
(including both work outside the home and housework)? 1- Not at all 2- A little bit
(including both work outside the home and housework)? 1-Not at all 2-A little bit 3-Moderately

These questions are about how you feel and how things have been with you **during the past 4 weeks**. For each question, please give the one answer that comes closest to the way you have been feeling.

How much of the time during the past 4 weeks...

	All of the time	Most of the time	A good bit of the time	Some of the time	A little of the time	None of the time
23. Did you feel full of pep?	 	O 2	3	 	 	 
24. Have you been a very nervous person?	 	O 2	3	4	 	 
25. Have you felt so down in the dumps that nothing could cheer you up?	O 1	O 2	3	4	 	O 6
26. Have you felt calm and peaceful?	 	O 2	3	 	 	O 6
27. Did you have a lot of energy?	 	O 2	3	 	O 5	O 6
28. Have you felt downhearted and blue?	1	O 2	3	4	 	 
29. Did you feel worn out?	 	O 2	3	 	 	O 6
30. Have you been a happy person?	 	O 2	3	 	 	O 6
31. Did you feel tired?	 	2	3	4	 	6
32. During the past 4 weeks , how me problems interfered with your soc						
1-All of the time						
2-Most of the time						
3 - Some of the time						
4-A little of the time						
5-None of the time						

How TRUE or FALSE is **each** of the following statements for you.

	Definitely true	Mostly true	Don't know	Mostly false	Definitely false
33. I seem to get sick a little easier than other people	 	O 2	3	4	O 5
34.1 am as healthy as anybody I know	O 1	O 2	3	4	 
35. I expect my health to get worse	O 1	O 2	3	0 4	 
36. My health is excellent	O 1	O 2	3	4	O 5

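### SF-36 items with a four-week recall are scored 14 days into each period, so week 2 scores are diluted and week 8 scores mix the two treatments

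*Combined protocol and SAP*

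**What the plan says.** Under Assessments/Indices: "The SF-36 will be evaluated at screening, week 2,4,6,8,10 and 12". The table of study visits and assessments shows the same visits.

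The form in Appendix B does not use one recall period throughout. Items 13 to 32 refer to the last four weeks; item 20, for example, begins "During the past 4 weeks, to what extent has your physical", and the block for items 23 to 31 is introduced by "How much of the time during the past 4 weeks". Items 3 to 12 ask about the present ("Does your health now limit you in these activities"), and items 1, 2 and 33 to 36 carry no four-week window.

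On timing, Overview of Trial Sequence tells patients to restart injections on day 6 after five days of washout, and adds: "The day he starts will be defined as week 6 period 2". Week 8 is therefore 14 days into period 2, just as week 2 is 14 days into period 1.

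The SF-36 is listed among the exploratory outcomes. The exploratory analysis uses descriptive statistics and "bivariate analyses of the values at each assessment and the change from baseline to each assessment". Nothing shortens the recall, sets weeks 2 and 8 apart or mentions the overlap.

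**The concern.** A 28-day question asked after 14 days of treatment must reach back to before that treatment began. In period 1 it reaches into untreated time. In period 2 it reaches through the washout into the period 1 treatment.

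The section on study drug expects no carry-over, on the strength of liraglutide's half-life. That argument concerns drug in the body. It does not cover what the patient is asked to remember.

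Aim 2 includes quality of life on liraglutide versus placebo, and aim 3 is to inform a larger trial. A week 8 score that blends both treatments could be read as little or no quality-of-life benefit when the questionnaire's window is the cause. If the last-observation-carried-forward rule in Data Analysis is applied to the SF-36, a missing week 10 score would be replaced by a week 8 score that mixes the treatments, and a missing week 4 score by a diluted week 2 score.

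**Working it through.** The plan gives no figure of its own here. The check is a count of days in the recall window.

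**Inputs**
- Recall window: 28 days, items 13 to 32 (Appendix B). That is 20 of 36 items.
- Days on current treatment: 14 at weeks 2 and 8, 28 at weeks 4 and 10, 42 at weeks 6 and 12, with the first period 2 dose defined as week 6.
- Washout: 5 days as instructed (Overview of Trial Sequence). Study Design makes this a minimum.
- Period 1: patients "will be randomized to either liraglutide or placebo treatment for 6 weeks (Period 1"), or 4 weeks with early crossover. Either way at least 28 days of period 1 treatment precede the washout.
- Visit windows: ±1 day at weeks 2 and 8; ±3 days at weeks 4, 6, 10 and 12.

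**Day count**

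Current = min(28, days on current treatment). Washout = min(28 − current, 5). Other treatment = 28 − current − washout. In period 1 everything outside current treatment is pre-treatment time.

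| Visit | Current treatment | Pre-treatment or washout | Other treatment |
|---|---|---|---|
| Week 2 | 14 (13–15) | 14 pre-treatment (15–13) | 0 |
| Week 8 | 14, or 50% (13–15) | 5 washout, or 18% | 9, or 32% (10–8) |
| Week 4 | 28 (25 if 3 days early) | 0 (3 pre-treatment) | 0 |
| Week 10 | 28 (25 if 3 days early) | 0 (3 washout) | 0 |
| Weeks 6, 12 | 28, even 3 days early | 0 | 0 |

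Early crossover at week 4 leaves the week 8 split at 14/5/9.

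**Effect on the contrast**

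Assumptions: equal weight on each recalled day, a constant liraglutide effect d from day 1, and no effect in washout.
- Week 8, placebo–liraglutide sequence: 14/28 = 0.50d recalled.
- Week 8, liraglutide–placebo sequence: 9/28 = 0.32d recalled, although the patient is now on placebo.
- Between sequences at week 8: 0.50d − 0.32d = 0.18d.
- Within patient, week 2 versus week 8: placebo–liraglutide 0.50d − 0 = 0.50d; liraglutide–placebo 0.50d − 0.32d = 0.18d; mean (0.50 + 0.18)/2 = 0.34d.
- Within patient, week 4 versus week 10: 28/28 − 0 = 1.00d in either sequence; 25/28 = 0.89d if the liraglutide visit is 3 days early.

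**Sensitivity to washout length w (up to 14 days, nominal visit day)**

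Other-treatment days at week 8 = 14 − w: 9 for w = 5, 7 for w = 7, 4 for w = 10, 0 for w = 14. The between-sequence contrast is [14 − (14 − w)]/28 = w/28 of d: 0.18, 0.25, 0.36 and 0.50.

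**Comparison instruments**

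The PROMIS incontinence items and PROBE (Appendices C and D) look back 7 days. With 13 to 15 days on treatment at weeks 2 and 8, their windows lie wholly within the current treatment.

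**The case against.** The case for leaving the plan alone is that the SF-36 is exploratory and reported visit by visit, not through the repeated-measures model specified for the primary and secondary outcomes. Weeks 4 and 10, the primary time points, are collected and nominally clean. PROMIS and PROBE cover weeks 2 and 8 with a suitable recall. All of this stands and keeps the point small. It does not remove it: the plan still calls for analysis at every assessment, without distinguishing these two visits.

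Several stronger readings are tempting, and the documents do not support them:
- A reader might infer that the whole SF-36 is affected. Sixteen items have no four-week window, so the fractions above apply only to items 13 to 32.
- A reader might take 0.18d as the crossover contrast. It is the between-sequence contrast at week 8, or the within-patient contrast in the liraglutide–placebo sequence alone; the within-patient mean is 0.34d.
- A reader might conclude that no washout could clear the overlap. About 14 days would, and the five-day minimum permits that. What the documents support is that the instructed five days do not.
- A reader might say that week 2 mixes treatments. Its off-treatment half is pre-treatment time, so it is only diluted.
- A reader might pair week 6 with week 12 as an equally clean comparison. The windows are clean but the patients are selected: those who cross over early have no period 1 week 6 visit, and week 10 non-responders are assessed at week 12 only for adverse events and concomitant medication.

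**Conclusion.** The concern holds for 20 of the 36 items at two visits. At week 2, half of the recall window is pre-treatment. At week 8, under the instructed washout, half is on the current treatment, 18% is washout and about 32% (8 to 10 days) is on the other treatment.

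The day counts follow from the documents. The sizes of 0.18d between sequences, 0.34d within patient and 1.00d for week 4 versus week 10 rest on the three stated assumptions. The constant-effect assumption is the weakest: the dose is stepped up over the first two weeks of liraglutide, although the protocol cites near-immediate effects at the lowest dose in ostomy patients. If the effect builds with dose, the early visits recover less of it than shown, and week 4 versus week 10 would also fall somewhat below 1.00d.

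This is a cheap correction to an exploratory outcome. It has no bearing on the primary outcome, the sample size or the significance level.

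**What to change.** Add to the exploratory analysis section:
- SF-36 scales built on the four-week-recall items are not used for treatment comparisons at weeks 2 and 8.
- Values from weeks 2 and 8 on those scales are not carried forward into week 4 or week 10.
- The SF-36 treatment comparison is week 4 versus week 10.
- SF-36 results at weeks 6 and 12 are descriptive only, because early crossover and early termination determine who is assessed then.
- Quality-of-life and symptom comparisons at weeks 2 and 8 rely on PROMIS and PROBE.

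The cost is a short addition to the analysis text; the treatment schedule is untouched. The form can still be collected at weeks 2 and 8 for the items without a four-week window. The price is that there is no early treatment comparison on the affected scales, and a patient who leaves before week 4 contributes nothing to the SF-36 comparison.
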